2.5 Preclinical Studies

Please refer to the IB for full details.

2.5.1 Primary Pharmacology of APR-246

APR-246 has demonstrated efficacy in various preclinical *in vitro*, *ex vivo*, and *in vivo* cancer models, as single substance as well as in combination with several conventional chemotherapeutics. In many of these models APR-246 has shown good potency and efficacy and unique pharmacological profile in comparison with conventional chemotherapeutic drugs.

APR-246 reduced cell viability in a dose-dependent manner being more potent in SaOS-2-His273 cells, expressing mutant p53 than in TP53 null cells (lacking p53 expression). It also reduced cell viability in a large number of other cancer cell lines with different TP53 status. In *ex vivo* experiments with primary cancer cells from patients with AML and ovarian cancer, APR-246 reduced cell viability and, in contrast to conventional drugs, was effective also in TP53 mutant cancer cells.

A large number of solid cancer cell lines with various cisplatin sensitivity and TP53 status, were investigated in combination studies with APR-246 and cisplatin. In the various resistant cell lines tested, platinum compounds and doxorubicin showed resistance, while the sensitivity for APR-246 was considerably less affected. Strong synergistic ($CI < 0.5$) effects with APR-246 were observed in all cell lines with homozygous hotspot TP53 mutations. These cell lines showed high levels of mutant p53 protein. Synergistic ($CI < 0.8$) or strong synergistic ($CI < 0.5$) effects were observed in cancer cell lines with frequently occurring TP53 mutations accumulating moderate levels of mutant p53. Variable rather than strong synergistic combination effects were observed in the cell lines with wild-type p53 and in those in which full length p53 protein is not detectable.

These results are consistent with the proposed dual mechanisms of action of APR-246, and show that APR-246 can exert its anticancer effects both in cells carrying wild type p53 and cells carrying mutant p53. Hence, both p53 dependent and independent apoptotic effects contribute to its efficacy.

Strong synergistic effects were also observed with APR-246 and cisplatin in the cisplatin-resistant ovarian carcinoma cell line OVCAR-3, carrying the TP53 hotspot mutation R248Q. APR-246 resensitized the OVCAR-3 cancer cells to cisplatin as well as to the anthracycline doxorubicin; the IC_{50} value of cisplatin was decreased 5-fold.

Strong synergistic effects of APR-246 the DNA-damaging compound doxorubicin was also seen in the doxorubicin-resistant A2780ADR ovarian cancer cell line.

2.5.2 Safety Pharmacology of APR-246

REDACTED

2.5.3 Pharmacokinetics

REDACTED

2.5.4 Toxicology

REDACTED

2.6 Previous Clinical Studies

The first clinical trial (APR-246-01) was conducted with APR-246 in patients with refractory hematological malignancies and prostate cancer. For further information please refer to the IB.

2.7 Rationale for Study in Platinum-Resistant HGSOE Population

HGSOE accounts for approximately 70% of epithelial ovarian carcinoma (EOC) in Europe and North America [10].

There are a number of active treatment options available for women with platinum-resistant EOC, including weekly paclitaxel, PLD [14] and topotecan, but the ideal treatment is not known (European Society for Medical Oncology [ESMO] EOC guidelines [15]). A Cochrane systematic review of trials (n = 1323) with platinum-resistant EOC concluded that topotecan, paclitaxel and PLD have similar efficacy, but different patterns of side effects [16]. The SmPC dose for PLD in breast and ovarian cancer is 50 mg/m² administered once every 4 weeks. A dose of 40 mg/m²/4

weeks will be used in this study, as this is the dose that is almost ubiquitously used in clinical practice and is the dose recommended by an international panel of experts [17].

APR-246 may offer an opportunity to improve current treatment of platinum-resistant HGSOc patients. The rationale for this derives from preclinical evidence that MQ (i.e., the active moiety of APR-246) induces apoptosis and cell death in cancer cells with mutant TP53 or otherwise non-functional p53.

2.7.1 Preliminary APR-407 Results and Rationale for Selected APR-246 Dose and Infusion Time

REDACTED

REDACTED

2.8 Characteristics of a Well-Conducted Trial

The following characteristics of an adequate and well-conducted trial will be implemented:

1. The Investigators will be well qualified by scientific training and experience.
2. Detailed electronic case report forms (eCRFs) will be completed for every patient.
3. Requirements for institutional ethics review as set forth by the appropriate Independent Ethics Committee (IEC), Title 21 Code of Federal Regulations (CFR) Part 56, the European Union Directive 2001/20/EC and its associated Detailed Guidances, European Union Good Clinical Practice (GCP) Directive 2005/28/EC, the International Conference on Harmonisation (ICH) Guideline for Good Clinical Practice, Sections 3 and 4, and the terms of the Declaration of Helsinki (2013), will be followed.
4. Requirements for informed consent in accordance with institutional guidelines, US Food and Drug Administration (FDA) requirements as specified in Title 21 CFR, Part 50, the European Union Directive 2001/20/EC and its associated Detailed Guidances, European Union GCP Directive 2005/28/EC, the ICH Guideline for Good Clinical Practice, Section 4.8, and the terms of the Declaration of Helsinki (2013), will be followed.
5. Safety data will be recorded and evaluated.
6. Routine monitoring visits will be conducted by the Sponsor's representative (Theradex[®]) to ensure data accuracy.
7. APR-246 accountability will be strictly maintained.
8. This trial will be conducted according to Good Clinical Practice (GCP), the protocol and applicable regulatory requirements.

3.0 TRIAL OBJECTIVES AND ENDPOINTS

3.1 Main Objectives and Endpoints

3.1.1 Primary Objective

- To assess the preliminary efficacy of APR-246 with PLD chemotherapy in patients with platinum-resistant HGSOc with mutated TP53

3.1.2 Secondary Objectives

- To evaluate the pharmacokinetics (PK) of APR-246 when administered with PLD chemotherapy
- To evaluate cardiac safety of APR-246 when administered with PLD chemotherapy
- To assess the safety and tolerability of APR-246 with PLD chemotherapy in patients with platinum-resistant HGSOc with mutated TP53
- To assess:
 - Duration of response (complete or partial response)
 - Progression-free survival (PFS) by assessment of cancer antigen 125 (CA-125)
 - PFS by RECIST 1.1
- To evaluate potential biomarkers and tumor activity based on CA-125
- To assess the biological activity in tumor and surrogate tissues.

3.1.3 Primary Endpoints

- Overall response rate according to RECIST 1.1

3.1.4 Secondary Endpoints

Secondary endpoints include the following:

- PFS rate, defined as the time from registration to the time of disease progression or relapse (according to RECIST 1.1 only) or death, or the date of last tumor assessment without any such event (censored observation)
- PK profile APR-246 and concentration in plasma

- Cardiac profile of APR-246 and concentration of PLD
- The safety profile (adverse events [AEs], laboratory assessments, physical findings and biomarkers) of APR 246 and PLD chemotherapy
- Duration of response (complete or partial response)
- Progression-free survival (PFS) by assessment of CA-125
- Evaluation of potential biomarkers
- Biological activity in tumor and surrogate tissues.

3.2 Sub-Study Objectives and Endpoints

Sub-study Objectives: Same as Main Study Objectives, except safety and tolerability, in addition to preliminary efficacy, are Primary Objectives.

Sub-study Primary Endpoint for safety and tolerability: The safety profile (adverse events [AEs], laboratory assessments, physical findings and biomarkers) of APR 246 with a shorter infusion and PLD chemotherapy.

4.0 STUDY DESIGN

4.1 Overview of Study Design

This study is an open-label, multicenter phase II study to assess whether patients with platinum-resistant TP53-mutated HGSOC will benefit from treatment with APR-246 and PLD chemotherapy. At least 25 evaluable patients will be included in this study. Patients may continue to receive treatment for as long as they are benefiting from it.

Different APR-246 infusion times will be explored. The Main Study will assess the standard 6 hour APR-246 infusion whilst the Sub-Study will explore shorter infusions (3 or 4 hour).

All patients will have pre-screening IHC to determine p53 status and therefore eligibility. Archived sections from the original tumor sample will be reviewed by a gynecological pathologist to confirm the diagnosis of HGSOC and positive IHC staining for p53. Patients without positive p53 staining will not be included.

Patients will receive standard 6 hour APR-246 infusion (fixed dose of 4.5 g APR-246) and PLD chemotherapy. After evaluation of the first six patients with the standard 6 hour infusion, a subgroup of up to 25 additional patients will be given the APR-246 dose over a shorter infusion time in order to evaluate this dosing schedule according to the same criteria as in the main study. The sub-study will be conducted in parallel with the main study.

At follow-up visits after the end of treatment, radiological tumor assessments should be performed every 8 weeks until protocol-defined progression occurs. For patients with stable disease, follow-up will take place until disease progression or until death.

All scans for each individual patient should have the same modality (CT or MRI) but CT is preferred.

A safety review committee (SRC) will evaluate the first 6 patients who receive the standard 6 hour infusion and the first 6 patients in the sub-study, to determine whether further patients can be enrolled and receive the same APR-246 infusion duration, at the same dose.

4.2 Registration of Patients

Upon completion of all screening evaluations, the center will register the patient using the Interactive Web Response System (IWRS). After successful completion of patient registration, a registration number will be issued.

Once the patient is registered through the IWRS, the patient is considered enrolled in the study. Specific instructions for the central enrollment and registration procedures are provided to the center in the study manual.

Registered patients will be assigned a unique patient identifier number. If a patient is withdrawn and replaced (as described in Section 5.3), the patient identifier number will not be reused.

4.3 Shipment of p53 samples

All archived pathology samples will be sent for centralized p53 analysis after registration and following local analysis. Labeling and shipment procedures will be provided in a separate laboratory manual.

4.4 Drug Products

4.4.1 Investigational Medicinal Product, APR-246

The study substance APR-246 (2-(hydroxymethyl)-2-(methoxymethyl)-1-azabicyclo [2,2,2] octan-3-one) is isolated as a white powder. APR-246 is prepared from quinuclidin-3-one in one reaction step using formaldehyde in methanol and in the presence of potassium carbonate (see IB). The IMP, APR-246 concentrate for solution for infusion, will be manufactured by Cobra BioPharma, Matfors, Sweden.

4.4.2 Reference Product PLD

PLD will be supplied by the hospital's pharmacy and will be administered in 28-day cycles.

4.5 Duration of Therapy

Patients will receive 28-day cycles of PLD chemotherapy with APR-246. Patients may continue to receive APR-246 with PLD for as long as in the Investigator's opinion they are benefiting from treatment and in the absence of disease progression and unacceptable toxicity. After the tenth 28-day cycle, data from assessments conducted within each treatment cycle will no longer be collected, but patients may continue to receive treatment after confirmation from the sponsor.

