 11. Is taking any concurrent (or within 4 weeks prior to registration) anti-cancer therapy, immunotherapy, radiotherapy, biological, or ancillary anti-cancer therapy, or any therapy that is considered to be investigational (i.e., used for non-approved indications(s) and in the context of a research investigation). Supportive care measures are allowed. Palliative limited radiation therapy for pain reduction is allowed.

Test Product, Dose and Mode of Administration:

Main Study:

Patients will receive a fixed dose of 4.5 g APR-246 (1.5 g of the dose during first 45 minutes followed by 3 g of the dose during 5 hours 15 minutes) on Days 1 to 4 with PLD 40 mg/m² on Day 4. The PLD administration to be given on Day 4 only should commence 2 hours after the start of the APR-246 infusion. Similarly for the following 28-day cycles, APR-246 will be administered on Days 1 to 4 with the PLD infusion on Day 4 starting 2 hours after the start of the APR-246 infusion. In all cycles, APR-246 will be administered as a 6-hour infusion.

Test Product, Dose and Mode of Administration:

Sub-Study:
 
Starting within 28 days of registration, patients will receive a fixed dose of 4.5 g APR-246 in a 2-step infusion, starting with a loading dose given during first 45 minutes followed by slower infusion of the remainder of the dose, during 2 hours 15 minutes on Days 1 to 4, with PLD 40 mg/m² on Day 4. The PLD administration to be given on Day 4 only should commence 2 hours after the start of the APR-246 infusion.
 
Other infusion durations and doses that may be explored in the Sub-Study are 4 hour 4.5 g, or 4 hour 3.7 g.

Duration of Treatment:
 
Patients will receive 28-day cycles of PLD chemotherapy with APR-246. Patients may continue to receive APR-246 with PLD for as long as in the Investigator's opinion they are benefiting from treatment and in the absence of disease progression and unacceptable toxicity. After the tenth 28-day cycle, data from assessments conducted within each treatment cycle will no longer be collected, but patients may continue to receive treatment after confirmation from the sponsor.

Reference Therapy, Dose and Mode of Administration:
 
Not applicable

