- **Tumor assessments:** CT scan/MRI at the end of Cycle 2 (within 4 days prior to the start of Cycle 3), at the end of Cycle 4 (within 4 days prior to the start of Cycle 5) and at the end of every two cycles of treatment thereafter. In patients who have discontinued therapy without progressive disease CT/MRI scans should be performed every 8 weeks until radiological progression.
- **ECG in selected patients:** Only at centers provided with Mortara ELI 150RX 12 lead ECG Recorder. 12-lead ECG, taken in triplicate:
 - Cycle 1 Day 1
 - Cycle 1, Day 4, optional, rhythm strip performed using limb leads of the 12-lead ECG machine, after the end of APR-246 infusion
 - Cycle 1 Day 19**
 - From Cycle 2 onwards performed on Day 1* each cycle

All recordings must be reviewed, dated and signed by the Investigator or an authorized subinvestigator. Refer to Laboratory Manual for detailed instructions.

- **12-lead continuous ECG Holter† in selected patients:** Only at centers provided with H12+ Holter Recorder. Cycle 1 only. Recorded for 24 hours, start prior to APR-246 administration on Day 1 and Day 4. Refer to Laboratory Manual for detailed instructions.
- **Pharmacokinetics:** At centers provided with H12+ Holter Recorder and Mortara ELI 150RX 12 lead ECG Recorder. Sampling for APR-246 in Cycle 1 on Day 1, 2, 4 and 5 (see Table 8); then sparse sampling for APR-246 on Day 1 and Day 4 from Cycle 2 onwards (see Table 9).†
- **Pharmacokinetics:** In all other patients: sparse sampling for APR-246 on Day 1 and Day 4 of all cycles (see Table 9).

† These assessments will be discontinued once sufficient evaluable data has been collected.

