7.3.4.6 Adverse Events Based on Examinations and Tests

The results from protocol-mandated laboratory tests, vital signs, ECGs and other safety assessments will be summarized in the clinical study report. Deterioration as compared to pretreatment in these parameters will therefore only be reported as AEs if they fulfill any of the criteria for a SAE, dose-limiting toxicity (DLT) or are the reason for modifying the study treatment unless clearly due to progression of disease under study (see Section 7.3.4.8).

If deterioration in a laboratory value, vital sign, ECG or other safety assessment is associated with clinical events, the clinical event will be reported as an AE and the associated laboratory result or other finding will be considered as additional information. Wherever possible the reporting Investigator will use the clinical, rather than the laboratory term (e.g., anemia versus low hemoglobin value). In the absence of clinical events, clinically relevant deteriorations in non-mandated parameters should be reported as AEs.

Deterioration of a laboratory value that is unequivocally due to disease progression should not be reported as an AE.

Any new or aggravated clinically relevant abnormal medical finding at a physical examination as compared with the pretreatment assessment will be reported as an AE.

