8.4.1 APR-246

A full PK profile will be taken during Cycle 1 from patients selected for ECG Holter testing (Table 8), followed by sparse PK sampling from Cycle 2 onwards (Table 9).

For all other patients, sparse PK sampling will be done from Cycle 1 until the last Cycle (Table 9).

The objective of the sparse PK sampling scheme is to enable construction of individual PK parameters (AUC and C_{max}) for correlation with efficacy and safety. The PK of APR-246 follow a bi-exponential decline and therefore a minimum of three samples are needed to construct the PK individual profiles.

The PK sampling scheme allows for some flexibility in the timing of the blood sampling and whenever possible time windows for sample collection are given. Nevertheless it is critical for the PK evaluation that the exact times of dose administration and PK sample collection are recorded on each occasion.

Table 8. PK Blood Sampling Time Points for APR-246 During Cycle 1 (Patients Selected for ECG Holter)

Day 1	Before infusion	0-2 hrs prior to APR-246 infusion
	During infusion	5-15 min prior to end of infusion
	After infusion	15 mins +/-3 min AFTER the end of infusion
		1 hr +/-5 min AFTER the end of infusion
		3 hrs +/-15 min AFTER the end of infusion
Day 2	Before infusion	0-30 min prior to APR-246 infusion
Day 4	Before infusion	0-30 min prior to APR-246 infusion
	During infusion	5-15 min prior to end of infusion
	After infusion	15 min +/-3 min AFTER the end of infusion
		1 hrs +/-5 min AFTER the end of infusion
		3 hrs +/-15 min AFTER the end of infusion
Day 5	No infusion	12-24 hrs AFTER the end of Day 4 infusion

Table 9. Sparse PK Blood Sampling Time Points for APR-246

D1 C1*-final cycle	Before infusion	0-2 hrs prior to APR-246 infusion
	At end of infusion	+/-5 min relative to the end of infusion
	After infusion	30-60 min AFTER infusion
D4 C1*-final cycle	Before infusion	0-2 hrs prior to APR-246 infusion
	At end of infusion	+/-5 min relative to the end of infusion
	After infusion	30-60 min AFTER infusion

*From Cycle 2 (C2) in patients selected for ECG Holter testing.

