9.4.2 Safety Data

Adverse Event Data

Safety data will be summarized for the safety evaluable population. These data will include AEs and laboratory parameters. AE terms will be coded using the Medical Dictionary for Drug Regulatory Activities (MedDRA; version 16.0 or higher). AEs will be summarized by body system, preferred term, severity and relationship to treatment. SAEs, deaths and AEs leading to early discontinuation of study drug will be summarized. DLTs will be provided in a separate listing by dose. Laboratory parameters will be summarized by maximum NCI CTCAE severity grade and also by change from study entry to scheduled time points using descriptive statistics. Laboratory parameter listings will

include the normal ranges for each parameter. Each value will be classified as falling above, below or within the normal range.

Data summaries will include only treatment-emergent AEs (TEAEs), defined as events occurring on or after Day 1 Cycle 1 up to and including 30 days after last dose.

Pharmacokinetic versus ECG Parameters

The relationship between changes in ECG parameters and plasma concentration of APR-246 will be explored where possible using non-linear mixed effects modelling.

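### Ending within-cycle data collection after Cycle 10 conflicts with the sparse PK schedule and can leave late laboratory deterioration unrecorded

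*Combined protocol and SAP*

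**What the plan says.** Section 4.5 and the synopsis (Duration of Treatment) state: "After the tenth 28-day cycle, data from assessments conducted within each treatment cycle will no longer be collected". Both add that "patients may continue to receive treatment after confirmation from the sponsor". Neither lists the assessments that stop.

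Other sections carry no Cycle 10 limit:

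- **PK.** Section 8.4.1: "For all other patients, sparse PK sampling will be done from Cycle 1 until the last Cycle (Table 9". Section 7.2.4 asks for "sparse sampling for APR-246 on Day 1 and Day 4 of all cycles (see Table 9". Table 9 runs to the final cycle.
- **Day 1 tests.** Section 7.2.4, which covers all cycles, schedules hematology, chemistry and CA-125 on Day 1 of each cycle. Of these, only CA-125 reappears at End of Treatment (7.2.5) and in follow-up (7.2.6).
- **LVEF.** Section 7.2.4 requires an echocardiogram before Cycles 3 and 6 and every third cycle after that. It also requires one before each PLD dose that takes lifetime anthracycline exposure above 450 mg/m². LVEF is not listed in 7.2.5 or 7.2.6.
- **Laboratory changes as AEs.** Section 7.3.4.6 notes that results of mandated tests will be summarized in the study report, and continues: "Deterioration as compared to pretreatment in these parameters will therefore only be reported as AEs if they fulfill any of the criteria" for an SAE or a DLT, or if they cause a change in study treatment. A clinical event linked to a laboratory change is reported in its own right.
- **Analysis.** Section 9.4.2: "Laboratory parameters will be summarized by maximum NCI CTCAE severity grade".
- **AEs and concomitant medication.** Sections 7.3.4.1 and 6.6 give these their own windows, ending 30 days after the last treatment.

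**The concern.** A site treating a patient in Cycle 11 cannot follow both Section 4.5 and the PK schedule.

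The laboratory data raise a further problem. The narrow AE rule in 7.3.4.6 is reasonable only while the results themselves reach the database. Section 4.5 removes the results after Cycle 10 but leaves the narrow rule in place. The maximum-grade summary would then cover Cycles 1 to 10 without saying so, and could understate late toxicity in the patients with the longest exposure.

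The objectives touched are safety (a secondary objective in the Main Study; in the Sub-Study a primary objective, with laboratory assessments named in the endpoint in Section 3.2), the secondary objective "To evaluate cardiac safety of APR-246 when administered with PLD chemotherapy" and the secondary endpoint "Progression-free survival (PFS) by assessment of CA-125".

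**Working it through.** The plan gives no figure to reproduce, so the check is a calendar for one worked case: 12 cycles, no delays, Day 1 tests done on Day 1.

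**Calendar.** Day 1 of cycle c = 28(c − 1) + 1. This gives Cycle 9 = Day 225, Cycle 10 = 253, Cycle 11 = 281, Cycle 12 = 309. Collection ends with Day 280 (10 × 28). The last APR-246 dose is Cycle 12 Day 4 = Day 312. The treatment-emergent window closes on Day 312 + 30 = 342. End of Treatment (30 ± 2 days after the last dose) is Day 340 to 344.

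**Hematology and chemistry.** The last collected result is Day 253.
- To last dose: 312 − 253 = 59 days. To close of window: 342 − 253 = 89 days.
- With the Cycle 12 Day 1 result collected: 312 − 309 = 3 days and 342 − 309 = 33 days.
- The Day 1 tests may be done up to 3 days early. If the Cycle 11 sample is drawn on Days 278 to 280 and kept, the gaps are 32 to 34 days (312 − 280, 312 − 278) and 62 to 64 days (342 − 280, 342 − 278).

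**CA-125.** The Day 281 and Day 309 values are not collected. The gap to End of Treatment is 340 − 253 = 87 to 344 − 253 = 91 days. With full collection the longest gap is 340 − 309 = 31 to 344 − 309 = 35 days. With an early Cycle 11 draw that is kept, it is 340 − 280 = 60 to 344 − 278 = 66 days.

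**LVEF, if Section 4.5 covers it.** Routine echocardiograms fall before Cycles 3, 6, 9 and 12. The pre-Cycle 9 result (Days 218 to 224) is collected; the pre-Cycle 12 result (Days 302 to 308) is not. At 40 mg/m² per cycle, with no prior anthracycline and no dose reduction, cumulative exposure is 11 × 40 = 440 mg/m² at Cycle 11 and 12 × 40 = 480 mg/m² at Cycle 12. The 450 mg/m² trigger is first passed at Cycle 12, so all of that patient's dose-triggered results fall after the cut-off.

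**PK (patients outside the Holter/Mortara centers).** Table 9 gives 3 samples on Day 1 and 3 on Day 4, or 6 per cycle. Twelve cycles give 72; Cycles 11 and 12 give 12, and 12/72 = 17%. Sixty remain.

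**Efficacy.** Nine months is 9 × 30.44 = 274 days, before Day 280, and the PFS clock starts earlier still, at registration. The end-of-Cycle-10 scan (Days 277 to 280) is collected. If the end-of-Cycle-12 scan (Days 333 to 336) were not, progression seen on it would be dated from the End of Treatment scan, 340 − 336 = 4 to 344 − 333 = 11 days later.

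**How many patients.** The documents do not say. As an assumption only, exponential PFS with a median of 3 to 8 months leaves 0.5^(9.2/3) = 12% to 0.5^(9.2/8) = 45% progression-free at Day 280 (9.2 months). That is about 3 to 11 of 25, an upper bound on those still treated, since some stop for other reasons.

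**The case against.** The limit looks deliberate. It appears twice in the same words, falls after the last planned PFS landmark, and can be read as pointing to the itemized list in 7.2.4. Much of this stands, and it rules out several stronger readings:

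- **That AE collection stops after Cycle 10.** A reader might infer this because 7.2.4 and Table 4 list AEs alongside cycle procedures. But AEs and concomitant medication have explicit windows past the last dose, and Section 4.5 does not revoke them.
- **That every asymptomatic laboratory change is lost.** Appendix V applies throughout treatment and requires prompt CRF entry when ALT or AST reaches 3 × ULN or bilirubin 2 × ULN. SAEs, DLTs and changes that modify treatment remain reportable. Section 7.3.4.6 also makes clinically relevant changes in non-mandated parameters AEs. That does not clearly close the gap, because 7.2.4 still mandates these tests in all cycles and nothing reclassifies them after Cycle 10.
- **That a planned CA-125 analysis is damaged.** Section 9.4.1 specifies no CA-125 PFS analysis, and CA-125 resumes at End of Treatment. Likewise, 9.4.2 names no LVEF analysis.
- **That the PK evaluation is compromised.** It is descriptive, and ten cycles already give 60 sparse samples per patient.

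One possible answer on PK fails. The early-stop footnote in 7.2.4 marks the Holter/Mortara-center sampling and depends on sufficient data, not on cycle number.

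The SAP still to be written could state where the laboratory summary ends, but it cannot recover results that were never collected.

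**Conclusion.** The point holds and is minor. The PK passages contradict Section 4.5 outright. Following Section 4.5 as written also drops Day 1 hematology, chemistry and on-treatment CA-125 from Cycle 11, while 7.3.4.6 still relies on the laboratory results being available. A non-serious deterioration that is not a DLT, does not modify treatment, has no clinical event and does not meet the Appendix V liver criteria can then go unrecorded, and the 9.4.2 maximum-grade summary would understate late toxicity.

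LVEF is conditional. The text does not settle whether Section 4.5 covers it; if it does, required cardiac results would be obtained but not collected.

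ORR and the 9-month PFS rate are essentially unaffected, and the effect on RECIST dating is a matter of days. The size rests on the 12-cycle, no-delay case and on an unknown number of patients treated beyond Cycle 10.

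**What to change.** - Amend Section 4.5 and the synopsis so that results of the hematology, chemistry, CA-125, LVEF and tumor assessments already required continue to be recorded through End of Treatment. Confirm there that the AE and concomitant-medication windows are unchanged.
- If laboratory collection is nevertheless to stop, state in 7.3.4.6 that clinically relevant deteriorations after Cycle 10 are reported as AEs, and in 9.4.2 that the laboratory summary ends at Cycle 10.
- Reconcile Sections 8.4.1 and 7.2.4 and Table 9 with Section 4.5 on when sparse PK sampling ends.

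The cost is a short amendment and modest extra data entry and monitoring for long-term patients. No procedure is added, because the tests are already scheduled.
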